- 8. The subject signs and dates a written, informed consent form and any required privacy authorization prior to the initiation of any study procedures.
- 9. A female subject of childbearing potential who is sexually active agrees to routinely use adequate contraception from signing of the informed consent throughout the duration of the study and for 30 days after the last dose of study drug.

Main Criteria for Exclusion:

Any subject who meets any of the following criteria will not qualify for entry into the study:

- 1. Subject has any current psychiatric disorder other than MDD (except nonprimary concurrent anxiety), other illness or condition which may compromise the study in the opinion of the investigator.
- 2. The subject has discontinued prior antidepressant treatment greater than 6 weeks prior to Screening.
- 3. Subject is considered to be at imminent risk for hospitalization due to severe depression in the opinion of the investigator. Recent hospitalization due to MDD within 3 months prior to Screening is also exclusionary.
- 4. The subject has a significant risk of suicide according to the investigator's clinical judgment or has made an actual suicide attempt in the previous 6 months prior to Screening or scores "yes" on Items 4 or 5 in the past 6 months on the Suicidal Ideation section of the C-SSRS.
- 5. The subject is considered to be treatment resistant, defined as patients with MDD who have not responded to 2 or more different antidepressants monotherapy studies of adequate dose and duration (6 weeks or longer) in their current episode. History of only responding to either combination or augmentation therapy in previous MDEs is also considered evidence of treatment resistant depression.
- 6. The subject has received any investigational compound within 30 days prior to Screening or 5 half-lives prior to Screening, whichever is longer.
- 7. The subject has previously or is currently participating in this study or another vortioxetine or LuAA21004 study.
- 8. The subject has participated in 2 or more interventional clinical studies in the year prior to Screening, or has participated in a clinical study for a psychiatric condition that is exclusionary per this protocol.
- 9. The subject is an immediate family member, study site employee, or is in a dependent relationship with a study site employee who is involved in conduct of this study (eg, spouse, parent, child, sibling).
- 10. The subject has 1 or more of the following:

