7.1 Inclusion Criteria

Subject eligibility is determined according to the following criteria prior to entry into the study:

- 1. Subject is a man or woman, aged 18 to 65 years, inclusive, and able to read and understand English.
- 2. Subject suffers from MDD as the primary psychiatric diagnosis.
- 3. Subject has been or is currently being treated with an approved antidepressant (monotherapy) for 6 weeks or longer at an adequate therapeutic dose. Subjects currently on an antidepressant at Screening will be discontinued in a manner that is consistent with labeling recommendations and conventional medical practice.
- 4. The subject's antidepressant treatment must be on-going at time of Screening, or have been discontinued within the 6 weeks prior to Screening.
- 5. Subject is considered appropriate for a change in antidepressant medication based on investigator judgment in collaboration with the subject.
- 6. Subject has scores on PHQ-9 \geq 5 and CGI-S \geq 4.
- 7. A female subject of childbearing potential who is sexually active agrees to routinely use adequate contraception* from signing of the informed consent throughout the duration of the study and for 30 days after the last dose of study drug.
- 8. In the opinion of the investigator, the subject is capable of understanding and complying with protocol requirements.
- 9. The subject signs and dates a written, informed consent form and any required privacy authorization prior to the initiation of any study procedures.

*Definitions and acceptable methods of contraception and Contraception and Pregnancy Avoidance Procedure are defined in Section 9.1.9. Pregnancy reporting responsibilities are defined in Section 9.1.10.

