9.1.9 Contraception and Pregnancy Avoidance Procedure

From signing of informed consent, throughout the duration of the study, and for 30 days after last dose of study medication, female subjects of childbearing potential must use adequate contraception. In addition, they must be advised not to donate ova during this period.

*Females NOT of childbearing potential are defined as those who have been surgically sterilized (hysterectomy, bilateral oophorectomy or tubal ligation) or who are postmenopausal (eg, defined as at least 1 year since last regular menses with a FSH>40 IU/L or at least 5 years since last regular menses, confirmed before any study medication is implemented).

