 - Progestogen-only hormonal contraception associated with inhibition of ovulation initiated at least 3 months prior to the first dose of study drug OR combined with a barrier method (male condom, female condom or diaphragm) if shorter till she has been on contraceptive for 3 months:
 - Oral.
 - Injectable.
 - Implantable.
- 2. Effective methods of contraception (there may be a higher than 1% failure rate) are:
 - Double-barrier method (contraceptive sponge, diaphragm or cervical cap with spermicidal jellies or creams PLUS male condom).
 - Progestogen only hormonal contraception, where inhibition of ovulation is not the primary mode of action PLUS condom with or without spermicide.
- 3. Unacceptable methods of contraception are:
 - Periodic abstinence (eg. calendar, ovulation, symptothermal, postovulation methods).
 - Spermicides only.
 - Withdrawal.
 - No method at all.

- Use of female and male condoms together.
- Cap/diaphragm/sponge without spermicide and without condom.
- 4. Subjects will be provided with information on highly effective/effective methods of contraception as part of the subject informed consent process and will be asked to sign a consent form stating that they understand the requirements for avoidance of pregnancy, donation of ova donation during the course of the study.
- 5. During the course of the study, regular urine hCG pregnancy tests will be performed only for women of childbearing potential. Women of childbearing potential will receive continued guidance with respect to the avoidance of pregnancy and ova donation as part of the study procedures. Such guidance should include a reminder of the following:
 - a) Contraceptive requirements of the study.
 - b) Reasons for use of barrier methods (ie, condom).
 - c) Assessment of subject compliance through questions such as:
 - i. Have you used the contraception consistently and correctly since the last visit?
 - ii. Have you forgotten to use contraception since the last visit?
 - iii. Are your menses late? (even in women with irregular or infrequent menstrual cycles a pregnancy test must be performed if the answer is "yes").
 - iv. Is there a chance you could be pregnant?

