Appendix C Elements of the Subject Informed Consent

In seeking informed consent, the following information shall be provided to each subject:

- 1. A statement that the study involves research.
- 2. An explanation of the purposes of the research.
- 3. The expected duration of the subject's participation.
- 4. A description of the procedures to be followed, including invasive procedures.
- 5. The identification of any procedures that are experimental.
- 6. The estimated number of subjects involved in the study.
- 7. A description of the subject's responsibilities.
- 8. A description of the conduct of the study.
- 9. A statement describing the treatment(s) and the probability for random assignment to each treatment.
- 10. A description of the possible side effects of the treatment that the subject may receive.
- 11. A description of any reasonably foreseeable risks or discomforts to the subject and, when applicable, to an embryo, fetus, or nursing infant.
- 12. A description of any benefits to the subject or to others that reasonably may be expected from the research. When there is no intended clinical benefit to the subject, the subject should be made aware of this
- 13. Disclosures of appropriate alternative procedures or courses of treatment, if any, that might be advantageous to the subject and their important potential risks and benefits.
- 14. A statement describing the extent to which confidentiality of records identifying the subject will be maintained, and a note of the possibility that regulatory agencies, auditor(s), IRB/IEC, and the monitor may inspect the records. By signing a written informed consent form, the subject or the subject's legally acceptable representative is authorizing such access.
- 15. For research involving more than minimal risk, an explanation as to whether any compensation and an explanation as to whether any medical treatments are available if injury occurs and, if so, what they consist of or where further information may be obtained.
- 16. The anticipated prorated payment(s), if any, to the subject for participating in the study.
- 17. The anticipated expenses, if any, to the subject for participating in the study.
- 18. An explanation of whom to contact for answers to pertinent questions about the research (investigator), subject's rights, and IRB/IEC and whom to contact in the event of a research-related injury to the subject.

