 - c) that personal information (including personal health information) may be added to Takeda's research databases for purposes of developing a better understanding of the safety and effectiveness of the study drug(s), studying other therapies for subjects, developing a better understanding of disease, and improving the efficiency of future clinical studies;
 - d) that subjects agree not to restrict the use and disclosure of their personal information (including personal health information) upon withdrawal from the study to the extent that the restricted use or disclosure of such information may impact the scientific integrity of the research; and

- e) that the subject's identity will remain confidential in the event that study results are published.
- 25. Female women of childbearing potential (eg, nonsterilized, premenopausal female subjects) who are sexually active must use highly effective contraception (as defined in the informed consent) from Screening throughout the duration of the study, and for 5 half lives PLUS 30 days after last dose. Regular pregnancy tests will be performed throughout the study for all female women of childbearing potential. If a subject is found to be pregnant during study, study drug will be discontinued and the investigator will offer the subject the choice to receive unblinded treatment information.
- 26. A statement that clinical trial information from this trial will be publicly disclosed in a publicly accessible website, such as ClinicalTrials.gov.

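### Appendix C sets a longer post-dose contraception period than the rest of the protocol, and Section 9.1.9.1 leaves the required standard unclear

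*Protocol*

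**What the plan says.** Appendix C of the protocol opens as a mandatory list: "In seeking informed consent, the following information shall be provided to each subject". Under item 25, women of childbearing potential who are sexually active "must use highly effective contraception (as defined in the informed consent) from Screening throughout the duration of the study", and then "for 5 half lives PLUS 30 days after last dose".

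The rest of the protocol gives a different end date and a different word for the standard:

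- Section 7.1, item 7, asks for adequate contraception "from signing of the informed consent throughout the duration of the study and for 30 days after the last dose of study drug".
- Synopsis (Section 2.0), inclusion item 9: the subject "agrees to routinely use adequate contraception from signing of the informed consent throughout the duration of the study and for 30 days", counted from the end of dosing.
- Section 9.1.9: "for 30 days after last dose of study medication, female subjects of childbearing potential must use adequate contraception".
- Appendix A, footnote (g), describes the consent statement on pregnancy and ova donation. It also runs to 30 days after the last dose.
- Section 9.1.10 requires immediate reporting of a pregnancy that occurs on treatment or within 30 days of the last dose.

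Section 9.1.9.1 deals with methods. Item 1 defines highly effective methods (under 1% failure a year) and presents its list as the complete set of acceptable methods. Item 2 then adds a second tier: "Effective methods of contraception (there may be a higher than 1% failure rate) are" followed by double-barrier methods and certain progestogen-only methods used with a condom. Unacceptable methods are listed separately in item 3. Item 4 says the information given during consent covers both tiers.

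**The concern.** Eligibility, consent, counselling and pregnancy reporting should all apply the same rule. Here a site that drafts its consent text from Appendix C arrives at a longer period than a site that drafts from Section 7.1 or Appendix A footnote (g). Section 15.2 makes the investigator responsible for the content of the consent form, and about 25 sites are planned, so the sites may not resolve the conflict in the same way.

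Two practical matters are at stake. First, under item 25 a woman would still be required to avoid pregnancy after the point at which the protocol ceases to require that a pregnancy be reported. Second, sites and monitors have no single text by which to decide whether a given method meets the requirement.

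**Working it through.** The protocol states no figure that needs reproducing. The check sets the current passages side by side and adds one line of arithmetic.

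| Place | Standard | Population | End, after last dose |
|---|---|---|---|
| Synopsis, item 9 | adequate | childbearing potential, sexually active | 30 days |
| 7.1, item 7 | adequate | childbearing potential, sexually active | 30 days |
| 9.1.9 | adequate | childbearing potential | 30 days |
| Appendix A (g) | acceptable methods | childbearing potential | 30 days (pregnancy and ova donation statement) |
| 9.1.10 | reporting rule only | any subject found pregnant | 30 days |
| Appendix C, item 25 | highly effective | childbearing potential, sexually active | 5 half-lives + 30 days |

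**Period.** Write t for the half-life in days.

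- Appendix C: 5t + 30 days.
- All other places: 30 days.
- Gap: (5t + 30) − 30 = 5t days, which is above zero for any t.

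The documents give no value for t. For illustration only, with assumed values:

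- t = 1: 5 + 30 = 35 days, a gap of 5 days.
- t = 3: 15 + 30 = 45 days, a gap of 15 days.
- t = 7: 35 + 30 = 65 days, a gap of 35 days.

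**Follow-up in the gap.** The disputed period starts when the 30 days end, so none of it falls within the reporting window of Section 9.1.10. Routine AE collection has already stopped at 4 weeks, or 28 days (Section 10.2.1.1). The safety call is planned at 28 ± 7 days after completion or withdrawal (Section 9.3.7), that is, 21 to 35 days. A late call could reach a few days into the gap; a call on the nominal day would precede it if the last dose coincides with completion or withdrawal.

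**Standard.** Section 7.1 does not define adequate itself and sends the reader to Section 9.1.9. Section 9.1.9.1 then allows two readings:

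- Item 1 governs. Only highly effective methods count, so adequate means highly effective and the body agrees with Appendix C.
- Items 2 and 4 govern. Second-tier methods also count. A woman using a double-barrier method would then meet Section 7.1 and fail item 25.

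The text does not say which reading is meant.

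**Population.** Item 25, the synopsis and Section 7.1 are limited to women who are sexually active. Section 9.1.9 has no such limit.

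**The case against.** Four arguments can be made on the other side.

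- *The body and Appendix C may not differ on the standard.* This stands in part. A reader might infer a clean contradiction, with the appendix strict and the body lenient. The documents do not support that, because item 1 of Section 9.1.9.1 can be read as imposing the same standard as item 25. The conflict over the standard begins inside Section 9.1.9.1.
- *Nobody has shown that participants were told conflicting things.* This stands. The consent form is not in the documents, and Section 15.2 requires the IRB or IEC and the sponsor to approve it before use. Only the inconsistency in the text that sites work from is established.
- *The longer period contains the shorter one, so following item 25 also satisfies the 30-day rule.* This is true of the period. A reader might go on to infer that 30 days leaves participants unprotected. Without a half-life the documents cannot support that either. What remains is the mismatch with the reporting window, and two different durations for sites to give.
- *Item 25 looks like template text.* It offers unblinded treatment information in an open-label study, which makes this plausible, although Section 9.1.10 has similar wording. Unadapted text under a mandatory heading still instructs sites, so this may explain the conflict but does not remove it.

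**Conclusion.** This is an internal inconsistency in current text. It does not depend on the amendment history. The conflict over duration is certain: item 25 exceeds every other stated post-dose period by 5 half-lives, and the excess falls outside the pregnancy-reporting window. Its length in days is unknown; the 5 to 35 days shown above rest on assumed half-lives of 1 to 7 days.

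The uncertainty over the standard is real but of a different kind, since Section 9.1.9.1 does not settle which tier is required.

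A reader might take the conflict to reach every enrolled woman of childbearing potential. Item 25 and Section 7.1 do not go that far, because both cover only those who are sexually active; Section 9.1.9 alone is broader.

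The point concerns participant protection and consistent conduct across sites. It has no bearing on the primary endpoint, the sample size or any planned analysis. It should be corrected, and it is inexpensive to correct.

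**What to change.** Reconcile Appendix C item 25 with the synopsis, Sections 7.1, 9.1.9, 9.1.9.1 and 9.1.10, and Appendix A footnote (g). The reconciled text should:

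- state one standard, and resolve within Section 9.1.9.1 whether the second-tier methods are permitted;
- state one population, with or without the limit to sexually active women;
- state one post-dose period, used alike in eligibility, consent, counselling and pregnancy reporting.

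Which standard and which period apply is a clinical decision for the sponsor, and this review takes no position on it. Consent forms in use should then be checked against the reconciled text.

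The cost is a protocol clarification and matching consent wording. No statistical section needs to change.

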Appendix D Investigator Consent to Use of Personal Information

Takeda will collect and retain personal information of investigator, including his or her name, address, and other personally identifiable information. In addition, investigator's personal information may be transferred to other parties located in countries throughout the world (eg, the United Kingdom, United States, and Japan), including the following:

- Takeda, its affiliates, and licensing partners.
- Business partners assisting Takeda, its affiliates, and licensing partners.
- Regulatory agencies and other health authorities.
- IRBs and IECs.

Investigator's personal information may be retained, processed, and transferred by Takeda and these other parties for research purposes including the following:

- Assessment of the suitability of investigator for the study and/or other clinical studies.
- Management, monitoring, inspection, and audit of the study.
- Analysis, review, and verification of the study results.
- Safety reporting and pharmacovigilance relating to the study.
- Preparation and submission of regulatory filings, correspondence, and communications to regulatory agencies relating to the study.
- Preparation and submission of regulatory filings, correspondence, and communications to regulatory agencies relating to other medications used in other clinical studies that may contain the same chemical compound present in the study drug.
- Inspections and investigations by regulatory authorities relating to the study.
- Self-inspection and internal audit within Takeda, its affiliates, and licensing partners.
- Archiving and audit of study records.
- Posting investigator site contact information, study details and results on publicly accessible clinical trial registries, databases, and websites.

Investigator's personal information may be transferred to other countries that do not have data protection laws that offer the same level of protection as data protection laws in investigator's own country.

Investigator acknowledges and consents to the use of his or her personal information by Takeda and other parties for the purposes described above.

Appendix E Detailed Description of Amendments to Text

This document describes changes in reference to Protocol Incorporating Amendment No. 1.

Page 2, Section 1.1 Contacts

Existing Text

Responsible Medical Officer	[name]
(carries overall responsibility for the	Takeda Pharmaceuticals USA
conduct of the study)	US Medical Affairs
	[name]

Revised Text

Responsible Medical Officer	[name]
(carries overall responsibility for the	Medical Head, CNS
conduct of the study)	Takeda Pharmaceuticals USA
	US Medical Office
	[name]

Rationale for Amendment

Change in personnel.

Page 3, Section 1.1 Contacts

Page 5, Investigator Agreement

Page 61, Section 12.2 Record Retention

Existing Text

• International Conference on Harmonisation E6 Good Clinical Practice: Consolidated Guideline.

Revised Text

[figure not shown]
• International **Council for** Harmonisation E6(**R2**) Good Clinical Practice: Consolidated Guideline.

Rationale for Amendment

[figure not shown]
ICH name has changed and guidelines have been revised.

Page 3, Section 1.2 Approval

Existing Text

Revised Text

Rationale for Amendment

Change in personnel.

Page 11, Section 2.0 Study Summary, Study Design, 5th Paragraph

Page 24, Section 6.1 Study Design, 9th Paragraph

Existing Text

A futility analysis will be performed at an interim analysis after approximately 60 subjects have completed Week 12.

Revised Text

A futility analysis **may** be performed at an interim analysis after approximately 60 subjects have completed **the study**.

Rationale for Amendment

Analysis will be completed once 60 subjects have completed the safety follow up.

Page 13, Section 2.0 Study Summary, Main Criteria for Exclusion, Criterion #4

Page 28, Section 7.2 Exclusion Criteria, Criterion #4

Existing Text

The subject has a significant risk of suicide according to the investigator's clinical judgment or has made an actual suicide attempt in the previous 6 months prior to Screening or scores "yes" on items 4 or 5 in the Suicidal Ideation section of the C-SSRS.

Revised Text

The subject has a significant risk of suicide according to the investigator's clinical judgment or has made an actual suicide attempt in the previous 6 months prior to Screening or scores "yes" on items 4 or 5 in the **past 6 months on the** Suicidal Ideation section of the C-SSRS.

Rationale for Amendment

The intent of this criterion is to exclude subjects who currently have significant risk of suicide (according to the investigator's clinical judgment), or made an actual suicide attempt in the previous 6 months prior to Screening, or within the same time frame have had active suicidal ideation with some intent to act (item 4 of CSSRS) or have had active suicidal ideation with specific plan and intent to act (item 5 of CSSRS). A lifetime "yes" answer to items 4 and 5 will not exclude the subject, but a "yes" answer to past 6 months for items 4 and 5 is exclusionary.

Page 17, Section 3.3 List of Abbreviations

New and Revised Text

ICH International Council for Harmonisation

STAR*D Sequenced Treatment Alternatives to Relieve Depression

US United States

WAIS-IV Wechsler Adult Intelligence Scale Fourth Edition

Rational for Amendment

Clarification of text

Page 20, Section 4.2 Rationale for the Proposed Study

Existing Text

Data from clinical studies regarding switching antidepressant medication rates is minimal and the rationale for the switch varies across studies [12]. Claims databases have shown switching rates for antidepressants have ranged from 2.78% to 13.7% [13,14]. The results of switching, in particular, multiple switching can lead to suboptimal outcomes for patients. Results of the STAR_D *project* showed that as the number of switches increased the burden of illness, including relapse rates, also increased. Relapse may trigger a pharmacologic switch [15]. Switching antidepressant agents has been shown to increase treatment costs and can be burdensome to the patient, so it is important to get the patient to the optimal treatment as early as possible in the therapeutic pathway [16].

Revised Text

Data from clinical studies regarding switching antidepressant medication rates is minimal and the rationale for the switch varies across studies [12]. Claims databases have shown switching rates for antidepressants have ranged from 2.78% to 13.7% [13,14]. The results of switching, in particular, multiple switching can lead to suboptimal outcomes for patients. Results of the **Sequenced Treatment Alternatives to Relieve Depression (STAR*D) study** showed that as the number of switches increased the burden of illness, including relapse rates, also increased. Relapse may trigger a pharmacologic switch [15]. Switching antidepressant agents has been shown to increase treatment costs and can be burdensome to the patient, so it is important to get the patient to the optimal treatment as early as possible in the therapeutic pathway [16].

Rational for Amendment

Clarification of text.

Page 22, Section 5.2.3 Additional Endpoints

New Text

• Summary of level of satisfaction with study treatment and the goal attainment approach among clinicians and subjects.

Rational for Amendment

Documentation of antidepressant change, and satisfaction with change in treatment was noted in Section 9.3, but was not listed in the table of procedures in error. Clinician and subjects satisfaction with GAS is being added to assess the GAS approach in clinical practice and to guide future GAS work.

Page 40, Section 9.1.7.5 Compa

Existing Text
Company Confidential Information

Revised Text

Rationale for Amendment

Company Confidential Information

Page 43, Section 9.1.9 Contraception and Pregnancy Avoidance Procedure

Existing Text

From signing of informed consent, throughout the duration of the study, and for 4 weeks after last dose of study medication, female subjects of childbearing potential must use adequate contraception. In addition, they must be advised not to donate ova during this period.

Revised Text

From signing of informed consent, throughout the duration of the study, and for **30 days** after last dose of study medication, female subjects of childbearing potential must use adequate contraception. In addition, they must be advised not to donate ova during this period.

Rationale for Amendment

To keep language consistent with inclusion criteria.

Page 44, Section 9.1.9.1 Definitions and Procedures for Contraception and Pregnancy Avoidance, Nonhormonal Methods

Existing Text

True sexual abstinence, only if this is in line with the preferred and usual lifestyle of the subject. True abstinence is defined as refraining from heterosexual intercourse during the entire period of the study, from 1 month prior to the first dose, throughout the duration of the study, and for 4 weeks after completion of the study.

CONFIDENTIAL

Revised Text

True sexual abstinence, only if this is in line with the preferred and usual lifestyle of the subject. True abstinence is defined as refraining from heterosexual intercourse during the entire period of the study, from 1 month prior to the first dose, throughout the duration of the study, and for 30 days after completion of the study.

Rationale for Amendment

To keep language consistent with inclusion criteria.

Page 45, Section 9.1.10 Pregnancy, 2nd Paragraph

Existing Text

If the pregnancy occurs during administration of active study medication, eg, after Visit 2 or within 4 weeks of the last dose of active study medication, the pregnancy should be reported immediately, using a pregnancy notification form, to the contact listed in Section 1.1.

Revised Text

If the pregnancy occurs during administration of active study medication, eg, after Visit 2 or within **30 days** of the last dose of active study medication, the pregnancy should be reported immediately, using a pregnancy notification form, to the contact listed in Section 1.1.

Rationale for Amendment

To keep language consistent with inclusion criteria.

Page 46, Section 9.1.11 PGx Sample Collection, 3rd Paragraph

Existing Text

Two whole blood samples (2.5 mL per sample) for RNA isolation will be collected at the Baseline Visit before dosing and at the Week 12/Early Termination (Visit 6) into plastic K₂EDTA spray-coated tubes, and stored under frozen conditions.

Revised Text

Two whole blood samples (2.5 mL per sample) for RNA isolation will be collected at the Baseline Visit before dosing and at the Week 12/Early Termination (Visit 6) into **PAXgene** tubes, and stored under frozen conditions.

Rationale for Amendment

Incorrect collection tube was listed.

Page 47, Section 9.3.1 Screening Visit 1 (Days -21 to -1)

Existing Text

Subjects will may be screened within 21 days prior to Baseline. Procedures to be completed during the Screening Visit are detailed in Appendix A. Subjects will be screened in accordance with predefined inclusion and exclusion criteria as described in Section 7.0. See Section 9.1.12 for

procedures for documenting screening failures. IxRT will be accessed for the subject screening number. The Screening and Baseline Visits may be combined if determined appropriate per the investigator. Any procedure that is to be performed at both visits should only be conducted once for a combined visit.

Revised Text

Subjects will may be screened within 21 days prior to Baseline. Procedures to be completed during the Screening Visit are detailed in Appendix A. Subjects will be screened in accordance with predefined inclusion and exclusion criteria as described in Section 7.0. See Section 9.1.12 for procedures for documenting screening failures. IxRT will be accessed for the subject screening number. The factors for determining a change/discontinuation from the prior antidepressant as assessed by the subject and by the investigator will be collected. The Screening and Baseline Visits may be combined if determined appropriate per the investigator. Any procedure that is to be performed at both visits should only be conducted once for a combined visit.

Rational for Amendment

This was noted at Baseline only, but should collected at Screening or combined Screening/Baseline Visit.

Page 48, Section 9.3.5 Final Visit or Early Termination

Existing Text

The Final Visit will be performed at Visit 7 (Week 12) or at Early Termination Visit. For all subjects receiving study drug, the investigator must complete the End of Study eCRF page. Procedures to be completed during Final Visit/Early Termination Visit are detailed in Appendix A.

For subjects who permanently discontinue study drug early, all Final Visit/Early Termination assessments detailed in Appendix A should be performed in close proximity to, or at the time of, study drug discontinuation.

The factors for determining a change/discontinuation from the prior antidepressant as assessed by the subject and by the investigator will be collected at the Final Visit and Early Termination (as applicable). Additionally at the End of Study Visit the Clinician satisfaction with the change in antidepressant will be collected.

Revised Text

The Final Visit will be performed at Visit 7 (Week 12) or at Early Termination Visit. For all subjects receiving study drug, the investigator must complete the End of Study eCRF page. Procedures to be completed during Final Visit/Early Termination Visit are detailed in Appendix A.

For subjects who permanently discontinue study drug early, all Final Visit/Early Termination assessments detailed in Appendix A should be performed in close proximity to, or at the time of, study drug discontinuation.

At the End of Study Visit the Clinician and subject satisfaction with the antidepressant treatment will be collected. In addition, Clinician and subject satisfaction with the GAS approach as a CONFIDENTIAL.

method for establishing treatment goals, evaluating progress towards treatment goals, and improving communication between clinicians and patients will be collected.

Rational for Amendment

Documentation of antidepressant change, and satisfaction with change in treatment was noted in Section 9.3, but was not listed in the table of procedures in error. Clinician and subjects satisfaction with GAS is being added to assess the GAS approach in clinical practice and to guide future GAS work.

Page 52, Section 10.1.4 SAEs, Criterion #5

Existing Text

Leads to a CONGENITAL ANOMALY/BIRTH DEFECT.

Revised Text

Is a CONGENITAL ANOMALY/BIRTH DEFECT.

Rationale for Amendment

Error in original text.

Page 64, Section 13.1.3 Effectiveness Analysis

New Text

Additional analysis will be performed for other additional endpoints, if necessary.

Rationale for Amendment

To allow for analysis of additional endpoints.

Page 64, Section 13.2 Interim Analysis and Criteria for Early Termination

Existing Text

No further subjects will be enrolled once approximately 60 subjects have completed their Week 12 visit. At this point, an interim futility analysis will be performed. If the futility criteria is met, the study will be stopped. Otherwise, an additional 60 subjects will be enrolled. The end of the study will be the date of the last safety follow-up visit of the last subject based either on the first 60 completed subjects or the final 120 completed subjects.

Revised Text

An interim analysis will be performed **once 60 subjects complete the study**. A **futility assessment will be done at this time.** If the futility criteria is met, the study **may** be stopped. The end of the study will be the date of the last safety follow-up visit of the last subject **completed**.

Rationale for Amendment

Analysis will be completed once 60 subjects have completed, but enrollment will not be stopped.

Page 74, Appendix A Schedule of Study Procedures Telephone Follow-up Window

Existing Text

Telephone Follow-up
Visit 8 Wk 16
Day 113 (± 3 Days)

Revised Text

Telephone Follow-up
Visit 8 Wk 16
Day 113 (± 7 Days)

Rationale for Amendment

Clarification of text to match the body of the protocol.

Page 75, Appendix A Schedule of Study Procedures

Existing Text

	Screening		Treatment						
	Visit 1 (a)	Baseline Visit 2 (a) Day 1	Visit 3 Wk 2	Telephone Contact Visit 4 Wk 4	Visit 5 Wk 6	Telephone Contact Visit 6 Wk 9	End of Study Visit 7 Wk 12 /Early Termination	Visit 8 Wk 16	
	Days -21 up to -1	Day 1	Day 15 (±3 Days)	Day 29 (±3 Days)	Day 43 (±5 Days)	Day 64 (±5 Days)	Day 85 (±5 Days)	Day 113 (± 3 Days)	
PTE/AE assessment	X	X	X	X	X	X	X	X	
Pregnancy testing and pregnancy avoidance counseling (e,f)	X	X	X		X		X		
Access IxRT for subject ID/ medication ID/subject status	X	X	X		X		X		
Dispense study drug		X	X		X				
Dose adjustment (as needed) (g)			X		X				

	Screening		Treatment					
	Visit 1 (a)	Baseline Visit 2 (a) Day 1	Visit 3 Wk 2	Telephone Contact Visit 4 Wk 4	Visit 5 Wk 6	Telephone Contact Visit 6 Wk 9	End of Study Visit 7 Wk 12 /Early Termination	Visit 8 Wk 16
	Days -21 up to -1	Day 1	Day 15 (±3 Days)	Day 29 (±3 Days)	Day 43 (±5 Days)	Day 64 (±5 Days)	Day 85 (±5 Days)	Day 113 (± 3 Days)
Study drug return/accountability/ compliance			X		X		X	

- (a) Screening and Baseline Visits may be combined as determined appropriate per the investigator. Any procedure that is to be performed at both visits should only be conducted once for a combined visit.
- (b) UDS to be done at Screening and Baseline. UDS kits will be supplied by the sponsor for the testing at the clinic. UDS results must be negative. This includes benzodiazepines and opiates for which there is no prescription (including oxycodone) at Screening and Baseline. Results must be confirmed prior to conducting the Baseline Visit.
- (c) Height at Screening only; weight at Screening, Baseline, and Week 12.
- (d) Subjects who signed an informed consent for pharmacogenomic testing will have blood samples for PGx analysis and these will be collected as follows: 2×3 mL for DNA on Day 1; 2×2.5 mL for RNA predose on Day 1 and at Week 12 (Visit 6).
- (e) Urine hCG pregnancy tests will be performed at Screening and Baseline and for all other visits during the Treatment Period for women of childbearing potential only. Serum hCG pregnancy tests will be performed at Baseline and End of Study/Early Termination visits for all females. For combined Screening and Baseline Visits, there will be 1 urine and 1 serum hCG. Subjects may be enrolled with a negative urine hCG; however if the serum hCG is positive the subject must be withdrawn from study drug immediately and withdrawn from the study as soon as possible.
- (f) Subject who are women of childbearing potential will be provided with information on acceptable methods of contraception as part of the subject informed consent process and will be asked to sign a consent form stating that they understand the requirements of pregnancy and donation of ova during the course of the study and for 4 weeks after the last dose of study drug.
- (g) Dose adjustments should occur during regularly scheduled visits, or subjects should return for an Unscheduled Visit.

Revised Text

	Screening		Treatment					
	Visit 1 (a)	Baseline Visit 2 (a) Day 1	Visit 3 Wk 2	Telephone Contact Visit 4 Wk 4	Visit 5 Wk 6	Telephone Contact Visit 6 Wk 9	End of Study Visit 7 Wk 12 /Early Termination	Visit 8 Wk 16
	Days -21 up to -1	Day 1	Day 15 (±3 Days)	Day 29 (±3 Days)	Day 43 (±5 Days)	Day 64 (±5 Days)	Day 85 (±5 Days)	Day 113 (± 7 Days)
Document factors for determining a change/discontinuation from prior antidepressant (e)	X							
PTE/AE assessment	X	X	X	X	X	X	X	X
Pregnancy testing and pregnancy avoidance counseling (f,g)	X	X	X		X		X	

	Screening	Treatment						
	Visit 1 (a)	Baseline Visit 2 (a) Day 1	Visit 3 Wk 2	Telephone Contact Visit 4 Wk 4	Visit 5 Wk 6	Telephone Contact Visit 6 Wk 9	End of Study Visit 7 Wk 12 /Early Termination	Visit 8 Wk 16
	Days -21 up to -1	Day 1	Day 15 (±3 Days)	Day 29 (±3 Days)	Day 43 (±5 Days)	Day 64 (±5 Days)	Day 85 (±5 Days)	Day 113 (± 7 Days)
Access IxRT for subject ID/ medication ID/subject status	X	X	X		X		X	
Dispense study drug		X	X		X			
Dose adjustment (as needed) (h)			X		X			
Clinician and subject satisfaction with change in antidepressant							X	
Clinician and subject satisfaction with GAS approach							X	
Study drug return/accountability/ compliance			X		X		X	

